4.6.2 Per Protocol Population (PPS)

The patients in the ITT population without any major protocol deviations as described in section 5. A patient that discontinuates from the study will typically be part of the ITT population but will not be included in the PPS population.

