4.6.3 Safety Analysis Population (SAF)

The safety analysis population will be the same as the ITT population.

5. Protocol Deviations

Deviations from the protocol including violations of inclusion/exclusion criteria will be assessed as “minor” or “major” in cooperation with the sponsor. Major deviations from the protocol will lead to the exclusion of a patient from the Per Protocol Set (PPS). Deviations will be defined prior to data base hard lock.

The following criteria will be used to exclude a patient from an analysis set:

- Incorrect diagnosis
- Any of the prohibited interventions/injuries for the target knee
- Missing more than 7 doses of MIV-711
- Discontinuation from the study

Note: this is not an exhaustive list of deviations, these are only the deviations specified per protocol. The discussion during the data review meeting post data base soft lock will review all deviations collected at each site and it will be decided to which analysis set each patient belongs.

6. General Considerations for Data Presentations

In this study IMP refers to any amount of the treatments defined in section 3.5, regardless of the time or period of administration.

Data for all patients enrolled in study MIV-711-202 who receives at least one dose of IMP will be presented in the data listings.

PAREXEL International Statistical Analysis Plan

Medivir
Protocol: MIV-711-202

Final 1.0
16 January 2018

A patient who is enrolled in study MIV-711-202 but does not receive IMP will be included in those data listings for which they have data but will be excluded from all data summaries. Data summaries will only include those patients that receive IMP.

For those listings or data summaries where baseline and change from baseline measurements will be presented, unless stated otherwise, the baseline assessment to be used for calculating change from baseline will be the last valid assessment prior to first dose of 200 mg MIV-711. Note that the change from baseline will be calculated also for visits prior to the baseline visit, not only for visits succeeding the baseline visit.

Data from both studies for patients enrolled in study MIV-711-202 will be included in the data listings, tables and figures, as appropriate.

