All pre- and post-dose assessments including unscheduled assessments will be included in the data listings. For unscheduled assessments collected pre-dose, the last assessment taken for a time point will be used in the data summaries (summary tables, figures, and statistical analysis); for all post-dose time points, the original assessment for any given time point will be used in the data summaries (summary tables, figures, and statistical analysis).

Descriptive statistics for observed values and derived change from baseline values will be tabulated by visit and study group. Continuous variables will be summarized by study group and visit, as appropriate, using descriptive statistics including: number of observations (n), mean (arithmetic), median, standard deviation (SD), minimum, and maximum. Frequencies and percentages will be used for summarizing discrete (categorical) data by study group and visit, as appropriate. The denominator used when calculating percentages will be the number of patients assessed at a particular combination of study group and study visit, as appropriate.

Safety and efficacy data that are reported as missing will be excluded from all descriptive and non-descriptive data analysis. There will be no imputation of any data. Observations that might be considered spurious (extreme relative to the majority of the data) will not be altered or removed from any presentation of the data, including the calculation of summary statistics (means, medians, etc.), unless approved by the sponsor.

For data listings, all raw data will be reported/displayed exactly as provided. For summaries of quantitative safety data, the minimum and maximum value will be reported exactly as the raw data are reported; measures of central tendency (means, medians) will be reported to one more decimal place than the raw data; measures of variance (SD) will be reported to two more decimal places than the raw data.

Unless stated otherwise there will be no adjustment for multiple comparisons.

PAREXEL International Statistical Analysis Plan

Medivir
Protocol: MIV-711-202

Final 1.0
16 January 2018

In all data presentations ‘Treatment’ will be defined as 200 mg MIV-711. Listings will include all patients and will be sorted by patient number and time point (where applicable). All derived data used in a data summary or statistical analysis will be listed.

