8.3.9 Brief Medication Questionnaire

Brief medication questionnaire results will be summarized for the number and percentage of patients reporting:

- each medication taken
- each indication
- combination of medication taken per indication
- compliance for each medication taken

Descriptive summary tables will be presented separately for Group A and Group B. Summary tables and listings for brief medication questionnaire will only be based on data from MIV-711-202 study.

9. Safety Analysis

For the safety outcomes, for study Group A, changes from baseline will be assessed using the Visit 2 baseline data from MIV-711-201. For study Group B, changes from baseline will be assessed using the Visit 2 data from Study MIV-711-202.

The change from baseline for visit X will be calculated as the (visit X – baseline visit)-difference in observed values. Note that the change from baseline will be calculated for all visits in study MIV-711-201 and study MIV-711-202 where the actual endpoint has been observed, i.e. not only for visits in study MIV-711-202 succeeding the baseline visit.

All safety summary tables will be based on the SAF population.

Descriptive summaries for safety will be presented by study group and visit, as appropriate.

PAREXEL International Statistical Analysis Plan

Medivir
Protocol: MIV-711-202

Final 1.0
16 January 2018

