9.6 Phone Call to Assess Safety

Results of this assessment will be listed for each patient and each visit.

PAREXEL International Statistical Analysis Plan

Medivir
Protocol: MIV-711-202

Final 1.0
16 January 2018

10. Reporting Output

The following details the requirements and specifications for the presentation of the tables, figures and listings (TFLs) as set out in the TFL shells.

The tables, listings, figures and any non-descriptive statistical analysis will be produced using Unix SAS[®] Software (Version 9.2 or higher). The REPORT procedure will be used to produce all tables and listings; SAS/GRAPH will be used to produce all figures.

Tables, listings, and figures will be produced in the order that they appear in the textual sections of the plan.

All tables, listings, and graphs will be produced to landscape orientation using Courier New 8pt font and will be incorporated into a MS Word document as a (RTF) rich text file (margins: top, left, right, and bottom: 1 inch). Details are provided below.

- A separate RTF document will be created for each table, figure and listing individually.
- All TFLs will be produced in a landscape format, as far as is feasible.
- The standard font size and font type are "8 point", "Courier New" for all TFLs.
- Every page of each output will contain a footer indicating the date and time when the output was produced.
- Page numbering of tables and listings will use the format "Page X of Y". Page numbering for figures will be consecutive integers.
- The ordering of visits will be chronological
- Footnotes are left justified.

PAREXEL International Statistical Analysis Plan

Medivir
Protocol: MIV-711-202

Final 1.0
16 January 2018

11. Summary Tables

TLF Number	Title
Table 14.1.1	Patient Disposition – All Enrolled Patients
Table 14.1.2	Demographics - Continuous Variables, ITT Population
Table 14.1.3	Demographics - Categorical Variables, ITT Population
Table 14.1.4	Prior Medications, ITT Population
Table 14.1.5	Concomitant Medications, ITT Population
Table 14.1.6	Flagged Prior Medications, ITT Population
Table 14.1.7	Flagged Medical History, ITT Population
Table 14.1.8	Dose Administration - Number and Percentage of Patients Who Received IMP by Visit, PPS Population
Table 14.1.9	Dose Administration – Summary of Drug Compliance, PPS Population
Pharmacodynamics	
Table 14.2.1.1	Imaging variables - MRI of Bone Area for the Target Knee Observed and Change from Baseline Summary, ITT Population

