Figure 14.2.3.2	Estimated change from visit 2 MIV-711-201 \pm 95% CI for NRS Items by Week and Group, ITT Population
Figure 14.2.4.1	Estimated Mean \pm 95% CI for WOMAC Items by Week and Group, ITT Population
Figure 14.2.4.2	Estimated change from visit 2 MIV-711-201 \pm 95% CI for WOMAC Items by Week and Group, ITT Population
Figure 14.2.4.3	Estimated Mean \pm 95% CI for Normalized WOMAC Scores by Week and Group, ITT Population
Figure 14.2.4.4	Estimated change from visit 2 MIV-711-201 \pm 95% CI for Normalized WOMAC Scores by Week and Group, ITT Population
Figure 14.2.5.1	Estimated Mean \pm 95% CI for NRS E-Diary by Week and Group, ITT Population
Figure 14.2.5.2	Estimated change from visit 2 MIV-711-201 \pm 95% CI for NRS e-diary by Week and Group, ITT Population
Figure 14.2.5.3	Estimated Mean \pm 95% CI for Percentage Score E-Diary Analgesic Usage by Week and Group, ITT Population
Figure 14.2.5.4	Estimated change from visit 2 MIV-711-201 \pm 95% CI for Percentage Scores of E-Diary Analgesic Usage by Week and Group, ITT Population
Figure 14.2.6.1	Estimated Mean \pm 95% CI for Efficacy Biomarkers by Week and Group, ITT Population
Figure 14.2.6.2	Box Plots of Time Integrated Concentrations and their Z-Scores for Efficacy Biomarkers from Serum and Urine Samples by Group, ITT Population

PAREXEL International Statistical Analysis Plan

Medivir
Protocol: MIV-711-202

Final 1.0
16 January 2018

Figure 14.2.7.1	Mean \pm 95% CI Profiles of Observed Systolic Blood Pressure by Week and Group, SAF Population
Figure 14.2.7.2	Mean \pm 95% CI Profiles of Observed Heart Rate by Week and Group, SAF Population
Figure 14.2.8.1	Mean (95% CI) Profiles of Observed QTcB Interval by Week and Group, SAF Population
Figure 14.2.8.2	Mean (95% CI) Profiles of Observed QTcF Interval by Week and Group, SAF Population

PAREXEL International Statistical Analysis Plan

Medivir
Protocol: MIV-711-202

Final 1.0
16 January 2018

13. Listings

TLF Number	Title
Listing 16.2.1.1	Patient Disposition
Listing 16.2.1.2	Patients Excluded from Analysis Populations
Listing 16.2.1.3	Enrolled Patients Who Did Not Meet All Eligibility Criteria
Listing 16.2.1.4	Exclusion Tests
Listing 16.2.2.1	Protocol Deviations
Listing 16.2.4.1	Demographics
Listing 16.2.4.2	Medical History
Listing 16.2.5.1	Prior and Concomitant Medications
Listing 16.2.5.2	Dose Administration at Clinic Visits
Listing 16.2.5.3	Dose Administration Compliance, ITT Population

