Listing 16.2.5.4	Dose Administration Overall Compliance at Visit 5, ITT Population
Listing 16.2.6.1	Numerical Rating Scale of Knee Pain
Listing 16.2.6.2	Numerical Rating Scale of Knee Pain Change From Baseline
Listing 16.2.6.3	Imaging Results Imorphics - MRI of Bone Area for the Target Knee, Observed and Change from Baseline
Listing 16.2.6.4	Imaging Results Imorphics - MRI of Cartilage Thickness for the Target Knee, Observed and Change from Baseline
Listing 16.2.6.5	Imaging Results Imorphics – Total BML Volume Observed and Change from Baseline
Listing 16.2.6.7.1	Other Imaging variables - Imorphics Bone Area
Listing 16.2.6.7.2	Other Imaging variables - Imorphics Bone 3D Shape
Listing 16.2.6.7.3	Other Imaging variables - Imorphics Cartilage Thickness
Listing 16.2.6.7.4	Other Imaging variables - Imorphics Cartilage Denudation
Listing 16.2.6.7.5	Other Imaging variables - Imorphics Cartilage Reference Bone Area
Listing 16.2.6.7.6	Other Imaging variables - Imorphics BML volume
Listing 16.2.6.7.7	Other Imaging variables - Imorphics Combined
Listing 16.2.6.8.1	Other Imaging variables - MOAKS Bone Marrow Lesion (BML) and Cyst
Listing 16.2.6.8.2	Other Imaging variables - MOAKS Cartilage Assessments
Listing 16.2.6.8.3	Other Imaging variables - MOAKS Hoffa-Synovitis/Effusion-Synovitis
Listing 16.2.6.8.4	Other Imaging variables - MOAKS Ligament Assessments
Listing 16.2.6.8.5	Other Imaging variables - MOAKS Meniscus
Listing 16.2.6.8.6	Other Imaging variables - MOAKS Osteophytes Assessments
Listing 16.2.6.8.7	Other Imaging variables - MOAKS Periarticular Features
Listing 16.2.6.9	Observed Raw ICOAP Scores
Listing 16.2.6.10	Transformed ICOAP Scores
Listing 16.2.6.11	Western Ontario and McMaster Index (WOMAC) - Pain Questions
Listing 16.2.6.12	Western Ontario and McMaster Index (WOMAC) - Stiffness Questions
Listing 16.2.6.13	Western Ontario and McMaster Index (WOMAC) - Difficulty Questions
Listing 16.2.6.14	Western Ontario and McMaster Index (WOMAC) Derived Scores and Change from Baseline
Listing 16.2.6.15	OARSI-OMERACT Responder Index

PAREXEL International Statistical Analysis Plan

Medivir
Protocol: MIV-711-202

Final 1.0
16 January 2018

Listing 16.2.6.16	OARSI-OMERACT Responder Index Change from Baseline and Percentage Change from Baseline Scores
Listing 16.2.6.17	Global Improvements
Listing 16.2.6.18	Quality of Life Patient Reported Outcomes - EQ-5D-5L
Listing 16.2.6.19	Quality of Life Patient Reported Outcomes Change from Baseline Scores - EQ-5D-5L

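### The only IMP dosing and compliance tables (14.1.8 and 14.1.9) use the PPS, so they cannot show poor compliance, and no table summarises dosing in the SAF

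*SAP*

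**What the plan says.** **Tables.** SAP section 11 lists two tables on IMP dosing: 14.1.8 (patients who received IMP, by visit) and 14.1.9 ("Dose Administration – Summary of Drug Compliance, PPS Population"). The shells in SAP section 14 repeat the PPS label for both and limit both to MIV-711-202 dosing. A footnote in shell 14.1.9 removes withdrawn patients.

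**PPS.** SAP section 5 includes "Missing more than 7 doses of MIV-711" among the criteria for leaving a patient out of an analysis set. Discontinuation is also on that list. SAP 4.6.2 says a discontinued patient "will typically be part of the ITT population but will not be included in the PPS population". Final membership is settled at the data review meeting.

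**Safety set.** SAP 4.6.3: "The safety analysis population will be the same as the ITT population", which means every enrolled patient with at least one dose. SAP section 9: "All safety summary tables will be based on the SAF population".

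**Text on dosing.** SAP 7.9 and Protocol 9.4 name no population for dosing or compliance. SAP 7.9 adds that compliance is not calculated for withdrawn patients, because the date of the last dose is not in the database.

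**Listings.** The matching listings in SAP section 13 are on the ITT: 16.2.5.3 ("Dose Administration Compliance, ITT Population") and 16.2.5.4 ("Dose Administration Overall Compliance at Visit 5, ITT Population"). Footnotes in both shells omit withdrawn patients.

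**Disposition.** SAP 7.1 and shell 14.1.1 tabulate completers, discontinuers, reasons for discontinuation and the size of each analysis set, by group, for all enrolled patients.

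**The concern.** The population of the compliance table is defined partly by compliance. A patient who misses too many doses leaves the table, so its mean, minimum and spread say little about how the drug was taken by the patients in the trial.

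The primary objective is safety and tolerability over 26+26 weeks, and the safety tables use every dosed patient. Reading an adverse-event frequency requires knowing how much drug those same patients took and for how long. The plan gives that summary only for a subset chosen for staying on treatment. Patients who interrupted or stopped are the informative ones for tolerability, and they are the ones left out.

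**Working it through.** The documents give no figure on this point to reproduce. The check is a reading of the indexes and shells plus simple arithmetic.

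**1. Is there another dosing table?** Tables 14.3.1.1 to 14.3.4.3 cover adverse events, laboratory values, vital signs and ECG. The number exposed in Table 14.3.1.1 is a percentage denominator, not an amount or duration. Table 14.2.8.4 mentions compliance, but the Brief Medication Questionnaire concerns concomitant medication. So 14.1.8 and 14.1.9 are the only ones.

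**2. Lowest value possible in Table 14.1.9.** Inputs: Visit 5 at Day 182 ± 7 (study schedule), one capsule a day, at most 7 missed doses (SAP section 5). Floor = (days − 7) / days.
- 175 days: 168/175 = 96.0%
- 182 days: 175/182 = 96.2%
- 189 days: 182/189 = 96.3%

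One further missed dose at 182 days gives 174/182 = 95.6%, and the patient leaves the table. The planned formula (Listing 16.2.5.4) is capsules used divided by days exposed, with capsules used taken as dispensed minus returned. An unreturned capsule therefore counts as taken, which can only raise the recorded figure.

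**3. What removes whom from Table 14.1.9.**
- Withdrawn patients are removed three times: by SAP 7.9, by the shell footnote and by the PPS label.
- Completers who missed more than 7 doses, or had another major deviation, are removed by the PPS label alone. No reason is given.

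In Table 14.1.8 there is no withdrawn-patient footnote, so the PPS label removes both kinds of patient.

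**4. Scale for patients who stop.** The documents give no withdrawal rate for this study. I assume 5% to 20%. At the top of the anticipated 50-80 patients, N = 80, that is 4 to 16 patients; at N = 50 it is 2.5 (2 or 3) to 10.

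Visit 5 row of Table 14.1.8 at N = 80:
- PPS: about 100%, because PPS patients are completers.
- SAF, full group N: 76/80 = 95% to 64/80 = 80%.
- SAF, patients assessed at the visit as denominator: 76/76 to 64/64, still 100%. This is one reading of SAP section 6 only ("The denominator used when calculating percentages will be the number of patients assessed at a particular combination of study group and study visit"); that sentence ends with an as-appropriate qualifier, so it leaves the choice open.

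Mean percent of planned doses in the SAF, with completers at 100% and stoppers assumed to take 25% to 75% of the course:
- 5% stopping: 0.95×100 + 0.05×25 = 96.25, to 0.95×100 + 0.05×75 = 98.75
- 20% stopping: 0.80×100 + 0.20×25 = 85, to 0.80×100 + 0.20×75 = 95

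Mean exposure if stoppers leave at Day 91 and the rest reach Day 182:
- 5% stopping: 0.95×182 + 0.05×91 = 177.5 days
- 20% stopping: 0.80×182 + 0.20×91 = 163.8 days

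The PPS would show about 182 days in both cases. For completers missing more than 7 doses, the documents support no estimate of number.

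**The case against.** The strongest reply is that little is concealed. Table 14.1.1 already shows by group how many patients completed, how many stopped and why, and a full-N Visit 5 row in Table 14.1.8 would largely repeat its completion row. SAP 7.9 gives a reason for leaving withdrawn patients out of compliance. Listings give the withdrawal day and date (16.2.1.1) and clinic doses (16.2.5.2). All of this stands, and it narrows the point. It does not supply doses or duration for patients who stopped, and it does not explain dropping completers with more than 7 missed doses.

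Several stronger readings are tempting, and the documents do not support them:
- **That drop-out is hidden.** Table 14.1.1 reports it.
- **That the protocol or SAP section 9 is breached.** Protocol 9.4 names no population, and these are not among the safety tables.
- **That adverse-event rates are distorted.** They stay on the SAF.
- **That the minimum in the planned compliance row would drop sharply on the SAF because of early stoppers.** SAP 7.9 and the footnote already exclude them. Under capsules/days, a patient who took every capsule until stopping would score about 100% if days ran to the last dose.
- **That limiting the tables to MIV-711-202 contradicts the rule of including both studies.** That rule also carries an as-appropriate qualifier.

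**Conclusion.** The point holds in a limited form. Tables 14.1.8 and 14.1.9 use a population that is wrong for their purpose, because a compliance table on the PPS has a built-in floor of about 96% and cannot show poor compliance. For the SAF, the plan lacks compliance in completers who missed more than 7 doses or had another major deviation, and the amount and approximate duration of dosing in patients who stopped.

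The floor assumes the 7-dose rule is applied as written over MIV-711-202; the data review meeting could decide otherwise. The size for stoppers rests on the assumed 5% to 20% stopping and 25% to 75% of the course taken. It ranges from a barely visible change (98.75% of planned doses) to a clear one (85%). No adverse-event percentage, estimate or test changes. What changes is the exposure against which the safety results are read.

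**What to change.** 1. Run Tables 14.1.8 and 14.1.9 on the SAF by group, with PPS versions as supportive.
2. In Table 14.1.8, state the full SAF group N as the denominator at every visit. A new population label alone would leave this open under SAP section 6.
3. In Table 14.1.9, keep the capsules/days compliance row for patients with a known last-dose date. For all dosed patients add capsules used as a percent of planned doses, and approximate days of exposure.
4. For withdrawn patients, use the drug accountability requested at early termination (Protocol 8.2) and the withdrawal date (SAP 7.1). Protocol 7.11 also plans an eCRF entry of the most recent dose with each biomarker sample, and that sampling is part of Visit 6. Check the SAP 7.9 statement on last-dose dates against that field, and use it only if it proves to be populated.
5. Amend the withdrawn-patient footnotes in Table 14.1.9 and Listings 16.2.5.3 and 16.2.5.4 to match, and footnote that exposure in withdrawn patients is approximate.
6. Optionally, add a 26+26-week exposure summary for Group A from the MIV-711-201 drug accountability (SAP 4.1). Rollover required completing Visit 8, so this would mainly show missed doses and the planned gap between studies.

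The cost is two population labels, a denominator note, amended footnotes and a few derived rows, plus a merge of MIV-711-201 data if the optional summary is wanted. It relies on data the protocol already planned to collect. Completeness is uncertain, because withdrawn patients are asked, not obliged, to attend the follow-up visit (Protocol 5.3).
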